10.7 Multiplicity Adjustment

Since Part 1 is a Phase-II proof-of-concept study, no adjustment will be made for the multiple comparisons in the primary endpoint (Arm A vs Arm E, Arm B vs Arm E, Arm C vs Arm A, Arm C vs Arm E, Arm D vs Arm A and Arm D vs Arm E). Each comparison will be controlled at 2-sided $\alpha = 0.10$.

In Part 2, the multiplicity adjustment to control the overall Type I error rate at 5% will include: (1) Bonferroni allocation of $\alpha = 0.017$ to each primary endpoint comparison: Arm K vs Arm N1, Arm L vs Arm N1, and Arm M vs N1; (2) a graphical approach to multiplicity adjustment to control the family-wise error at 0.05 (see Figure 6). The same method will be used in the Part 2 Alternate Scenario, with comparisons between Arms K-M and Arm N2.

[figure not shown]

Figure 6. Graphical Approach to Multiplicity Control in Part 2

Of note, the parallel graphical approach above shows how the α is passed to the next comparison if the null hypothesis is rejected.⁸¹

In the Alternate Scenario of Part 2, the primary endpoint for satisfying the combination rule in Part 1 continued in Part 2 (combination rule endpoint) is conducted at 2-sided $\alpha = 0.10$ with no need to adjust for multiplicity per Section 5.5.2 of the European Medicines Agency Guideline on Multiplicity Issues for Clinical Trials.⁸²

10.8 Statistical Analysis of Safety

All safety analyses will be performed on the Safety Population, which consists of all subjects who received at least one dose of IMP. Safety will be assessed by AEs, laboratory tests, vital signs, and ECG variables. Details of the analyses will be provided in the Statistical Analysis Plan.

AEs will be coded using the Medical Dictionary for Regulatory Activities (MedDRA). A TEAE is defined as an AE with an onset date that is after the first intake of IMP and no more than 30 days after the last intake of IMP. The number and percentage of subjects experiencing TEAEs will be tabulated using MedDRA system-organ class and preferred term, as well as by severity and by relationship to the IMP as assessed by the Investigator. Summaries of SAEs, deaths, AEs leading to discontinuation will also be provided.

For laboratory test and vital signs variables, mean change from baseline and percentage of subjects with on-treatment laboratory values of CTCAE 5.0 adapted scale grade 3 or 4 will be summarised.

10.9 Interim Analysis of Part 1 and DSMB Recommendation to Proceed to Part 2

Once subjects in Part 1 have completed or prematurely discontinued the study, up to and including nodulectomy at 6 months, a database lock for Part 1 database and an interim analysis of data from Part 1 will be conducted by the Sponsor and the randomisation code unblinded. The unblinded data will be reviewed by the Sponsor and the DSMB (see Section 13.3), for futility and risk/benefit ratio. Taking into account the recommendations of the DSMB, especially regarding the safety assessment of the data, the Sponsor will decide whether or not to proceed to Part 2, and with which dose regimens.

Selection of up to two acceptable/suitable doses / regimens for Part 2 will be based on analysis of all of available unblinded data from Part 1, including safety and tolerability of ABBV-4083 and ABBV-4083 + albendazole, *Wolbachia* depletion, disruption of embryogenesis and an exploratory surrogate marker, microfilaria *Wolbachia*, observed at Months 3 and 6.

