In order also to assess the effect of a dose of ivermectin at Month 6, participants will be randomised into four treatment arms, with the best candidate based on Part 1 results administered with ivermectin and with ivermectin placebo at Month 6.

Within each treatment arm, subjects will be stratified by the number of operable sites with onchocercomata and by mean screening skin mf. There will be four strata, i.e. 1 site and less than or equal to 5 mf/mg, more than 1 site and less than or equal to 5 mf/mg, 1 site and more than 5 mf/mg, more than 1 site and more than 5 mf/mg.

A total of either 294 subjects (Base Scenario) or 336 subjects (Alternative Scenario) will be recruited. The Base Scenario will be employed:

- if neither Arm C nor Arm D from Part 1 is selected for continued enrolment in Part 2, or
- if either Arm C and/or Arm D in Part 1 is selected for continued enrolment in Part 2 and Arm C and/or Arm D has demonstrated superiority over both Arm E and Arm A in Part 1.

[figure not shown]
The Alternative Scenario will be employed if either Arm C and/or Arm D in Part 1 is selected for continued enrolment in Part 2, but Arm C or Arm D in Part 1 has not demonstrated statistical superiority over both Arm E and Arm A.

In the Base Scenario, subjects will be randomised continuously 2:2:2:1 into one of four parallel treatment arms until group size is achieved:

- Arm K (n = 84): initial treatment with an active regimen selected from Part 1, followed by ivermectin at Month 6;
- Arm L (n = 84): initial treatment with the same active regimen selected from Part 1 as Arm K, followed by ivermectin matching placebo at Month 6;
- Arm M (n = 84): initial treatment with a second active regimen selected from Part 1, followed by either ivermectin or ivermectin matching placebo at Month 6 (decision to be made prior to Part 2);
- Arm N1 (n = 42): initial treatment with ABBV-4083 matching placebo and albendazole matching placebo, followed by ivermectin at Month 6.

Details of timing and sequence of investigations and measures are provided in the Schedule of Events (see Appendix 2). The overall design for Part 2 Base Scenario is presented in Figure 2.

Figure 2. Overall Design for Part 2 - Base Scenario

4083 = ABBV-4083; Alb = albendazole; d = days; D = (study) day; IVM = ivermectin; M = month; Pbo = placebo

In the Alternate Scenario, subjects will be randomised continuously 1:1:1:1 into one of four parallel treatment arms until group size is achieved:

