- · an IMP-related treatment-emergent AE leading to discontinuation, i.e. considered as having a reasonable possibility of being related to any of the IMPs, and with onset between Day 0 and 30 days after the end of treatment;
- a severe or serious IMP-related treatment emergent AE, i.e. considered as having a reasonable possibility of being related to any of the IMPs, and with onset between Day 0 and 30 days after the end of treatment;
- a Grade 3 or 4 ALT elevation during treatment, defined as between Day 0 and 2 days after the end of treatment; ALT elevations will not additionally be counted as AEs described in the previous two criteria, although they may be reported as AEs.

The SRC and DSMB will continue to monitor the toxicity criteria in Part 2, and the safety results will be cumulative from Part 1 to Part 2. That is, subjects with an event meeting the toxicity criteria during Part 1 will still count in Part 2 for the same treatment, as if the study was not paused between Part 1 and Part 2. If > 10% of subjects in any regimen meet the toxicity criteria across Parts 1 and 2, the regimen will halt but dose adjustment will not occur in Part 2. Safety will be reviewed by the SRC and DSMB using the same criteria for any arms in Part 1 that are restarted using the 300 mg ABBV-4083 dose.

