6.1 Inclusion Criteria

To be eligible for the study, subjects must satisfy all of the following inclusion criteria.

1. Written, signed (or thumb-printed) and dated informed consent, after having the opportunity to discuss the study with the Investigator or a delegate.

- 2. Men and women with *Onchocerca volvulus* infection, 18 to 65 years of age inclusive at time of Screening:
 - i. Presence of at least one excisable subcutaneous nodule/onchocercoma detected on palpation;
 - ii. *O. volvulus* infection diagnosed by skin snip method: documented mf-positivity on skin assessment on at least 2 out of 4 skin snips.
- 3. Body weight > 40 kg at Screening.
- 4. For women of child-bearing potential (WOCBP), (see Section 8.2), acceptance of the requirement to use a highly effective form of birth control (see Section 8.2 and Appendix 7) effective from Day 0 until at least 1 month after the final intake of IMP (Part 1: day 43; Part 2: 1 month after the administration of ivermectin or matching placebo at the Month 6 visit). Choice of birth control method must be clearly documented.

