In the Alternative Scenario, subjects will be randomly assigned 1:1:1:1 under double blind to Arms K, L, M and N2.

7.3.2.2 IMP Administration in Part 2

The IMP ABBV-4083 will be administered as 100-mg capsules or matching placebo capsules. The IMP albendazole will be administered as over-encapsulated 400-mg tablets or matching over-encapsulated placebo .

The IMPs ABBV-4083, albendazole and both matching placebo will be administered once daily by the oral route and are to be taken with food (See Section 9.2.8 for details).

The IMP ivermectin or matching placebo will be administered at the approved single oral dose of $150 \mu g/kg$ body weight per Table 5 as a single administration at Month 6. It will be administered to subjects on fasting conditions with water.

All IMPs will be administered at the investigational centre at approximately the same time each morning, and intake of the IMP will be directly observed by the study personnel.

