For the Part 2 combination rule hypothesis in the Alternate Scenario that compares the proportion of live female adult worms without Wolbachia at Month 6 between the combination arms of ABBV-4083 + albendazole for 7 days (Arm K plus Arm L) and the ABBV-4083 single drug arm (Arm N2), 17 subjects per each of Arms K and L for a total of 34 subjects in Part 2 in addition to the 25 subjects per arm in Part 1 will be able to provide an overall power of 96% to detect the difference between the combination arm where 90% of worms are without Wolbachia and the single drug arm where 70% of worms are without Wolbachia (2-sided α =0.10) in either Part 1 or Part 2, using an inverse normal combination test that combines the pvalues of alternating logistic regressions that use data from Part 1 only and Part 2 only. The assumption for the number of worms in each subject in Part 2 is adjusted to a multinomial distribution with probability = (0.22, 0.18, 0.17, 0.16, 0.08, 0.06, 0.06, 0.03, 0.02, 0.02) for values (1, 2, 3, 4, 5, 6, 7, 8, 9, 10) in order to account for the design that only worms from one nodule per subject in Part 2 will be used for this analysis. If Part 1 Arm B of ABBV-4083 for 14 days is used for Arms K and L of Part 2, Arm M would be the 4083/albendazole combination that is compared to Arm N2. 17 subjects in Arm M Part 2 in addition to the 25 subjects per arm in Part 1 will be able to provide an overall power of 95% using the same method. Assuming 17% of the subjects per arm drop out by Month 6, the enrolment in the alternate scenario will require at least 25% of subjects of those retained to Month 6 nodulectomy to have > 1 nodule site in the arms used to test this hypothesis to obtain the power shown above.

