- 11. The Investigator will arrange for a highly effective form of birth control (as detailed in Section 8.2) if required. Must be discussed at screening and checked within 2 days prior to the first intake of IMP and checked at the time-points indicated and documented. In the event of delayed menstrual period for over one month between menstruations, confirmation of absence of pregnancy with a pregnancy test is mandatory. This recommendation also applies to WOCBP with infrequent or irregular menstrual cycles.
- 12. Supine blood pressure (SBP, DBP), supine heart rate, respiratory rate and temperature.
- 13. Ophthalmological findings from examinations including ocular symptoms, ocular examinations including ocular alignment, mobility and pupillary response, visual function (visual acuity, visual field, colour vision), retinal examination and fundus photography, slit lamp examination of anterior and posterior segment and intraocular pressure. Eye microfilarial count and data for clinical outcomes in the eye will be recorded during the ophthalmological examination.
- 14. Assessments for clinical outcomes in the skin (see Study Operations Manual for details) to be performed during physical examinations where the time-points coincide.
- 15. ECGs will be recorded in triplicate (with 1 minute between recordings) except at D3, which will be single. ECGs will be performed 1-2 hours after intake of the IMP. ECG at early termination is only applicable if early termination is before Month 3.
- 16. Blood and urine samples for clinical laboratory safety tests (haematology, biochemistry, & urinalysis (plus urine microscopy where indicated if urinalysis is abnormal and clinically significant).
- 17. IMPs will be administered daily from D0 to D13 on site. IMPs dispensation will be done on D0, D3 and D7 via the IRT system.
- 18.Administration of ivermectin to all subjects. Only after completion of all the procedures of the 6-month follow-up visit, and after nodulectomy and negative pregnancy test. It can also be administered at the early termination visit at the discretion of the Investigator. Ivermectin will also be available for administration as Rescue Medication, at the Investigator's discretion, in the event of clinically significant worsening of symptoms and/or signs related to onchocerciasis at any time during the study.18.AE monitoring will be performed as specified in Section 9.3.4 and will include scheduled questioning at the indicated time-points.

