- 13. Ophthalmological examinations: full ophthalmological examination includes ocular symptoms, ocular examinations including ocular alignment, mobility and pupillary response, visual function (visual acuity, visual field, colour vision), retinal examination and fundus photography, slit lamp examination of anterior and posterior segments and intraocular pressure. Eye microfilarial count and data for clinical outcomes in the eye will be recorded during the ophthalmological examination.
- 14. Assessments for clinical outcomes (see Study Operations Manual for details) in the skin to be performed during physical examinations where the time-points coincide.
- 15. 12-lead ECGs will be recorded in triplicate with 1 minute between recordings at all time-points. ECGs will be performed 1-2 h after intake of the IMP. ECG at early termination is only applicable if early termination is before Month 3.
- 16. Blood and urine samples for clinical laboratory safety tests (haematology, biochemistry & urinalysis (plus urine microscopy where indicated if urinalysis is abnormal and clinically significant).
- 17. IMPs will be administered daily on site and IMPs dispensation will be done via the IRT system. Treatment duration and IMPs dispensation scheme will be confirmed before start of the Part 2, depending on the regimen selected.
- 18. Administration of ivermectin must be only after completion of the procedures scheduled at the visit (including nodulectomy where scheduled), and after a negative pregnancy test. Rescue medication (ivermectin) will be offered at the investigator discretion to administer if worsening symptoms and/or signs related to onchocerciasis at any time throughout the study and/or to patients with increased mean microfilaria in the skin at Month 18, compared to the Month 12 mean value.
- 19. AE collection from signature of Informed Consent onwards. AE monitoring will be performed as specified in Section 9.3.4 and will include scheduled questioning at the indicated time-points.
- 20. In the event of certain AEs considered to be associated with the IMP, additional examinations may be conducted in order to better interpret the AE, including safety laboratory, PK, ophthalmological, physical, neurological and parasitological (eye and skin) examinations.

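### In Part 2 the single treatment-emergent AE window makes an event between about Day 37–44 and Month 6 count only if the subject later takes the Month 6 dose, and it pools ivermectin reactions with those to the initial regimen

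*Protocol*

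**What the plan says.** Protocol 10.8 has one TEAE definition for the whole study: onset "after the first intake of IMP and no more than 30 days after the last intake of IMP". SAP 10.2.1 repeats the 30-day rule, but that SAP covers Part 1 only.

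In Part 1 all IMP ends together: "IMPs will be administered daily from D0 to D13 on site" (Protocol Appendix 1, footnote 17). Part 2 differs. Section 7.3.2.2 names the Month 6 dose as an IMP: "The IMP ivermectin or matching placebo will be administered at the approved single oral dose". Section 6.1 treats it as the final intake when it sets the end of contraception: "Part 2: 1 month after the administration of ivermectin or matching placebo at the Month 6 visit"; section 8.2 does the same. Section 10.2 also makes the Month 6 dose part of treatment completion in Part 2. Rescue and post-study ivermectin are not IMP (8.3), so they do not move the window.

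What is given at Month 6 differs by arm. In the Base Scenario (3.3), Arm K receives ivermectin and Arm L receives placebo after the same initial regimen. Arm M is undecided, and Arm N1 is "initial treatment with ABBV-4083 matching placebo and albendazole matching placebo, followed by ivermectin at Month 6".

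**The concern.** A safety classification should depend on what has happened up to the event. Here the status of an event at Month 3 is settled three months later by whether another dose is taken. That later dose may depend on the event. Section 6.5.2 allows IMP to be stopped if continuing would be harmful, with the subject remaining in follow-up. An AE after the short window that leads to the Month 6 dose being withheld, or to the subject leaving, therefore cannot be treatment-emergent.

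The second problem needs no attrition. One long window puts reactions to ABBV-4083 or albendazole and reactions to ivermectin in the same count. Section 3.5.1.4 says that Mazzotti reactions may occur with ivermectin and are not expected with ABBV-4083. The TEAE tables would then mix the effect of the initial regimen with the effect of the Month 6 allocation.

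**Working it through.** **1. The documents' own day count.** The last IMP day in Part 1 is Day 13, and 13 + 30 = 43. This matches the day 43 that Protocol 6.1 gives for one month after the final intake.

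**2. The same rule in Part 2.** The length of the initial course is still open: "Treatment duration and IMPs dispensation scheme will be confirmed before start of the Part 2" (Appendix 2, footnote 17). I take Day 6 to Day 13 as the range for the last initial intake, and 30.44 days per month.

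| Subject | Last IMP | Window ends |
|---|---|---|
| No Month 6 dose, 7-day course | Day 6 | 6 + 30 = Day 36 |
| No Month 6 dose, 14-day course | Day 13 | 13 + 30 = Day 43 |
| Month 6 dose at nominal time | Day 183 | 183 + 30 = Day 213 |
| Month 6 dose at −1 / +1 month | Day 152 / 213 | Day 182 / 243 |

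The Month 3 visit (±1 week) falls on Day 84–98. An event found there is a TEAE in the last two rows and not in the first two. The same holds for any onset from Day 37 or 44 up to the Month 6 visit.

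**3. Ceiling on the number of subjects.** Section 10.3.2 has "Assuming 17% of the subjects per arm drop out by Month 6". This gives 0.17 × 84 = 14.3 per active arm and 0.17 × 42 = 7.1 in N1. It is a ceiling, because subjects who leave before Day 44 lose nothing under the rule.

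**4. Subjects who lose their only TEAE.** Assumptions, not taken from the documents: departures uniform over Day 0–183 and independent of AEs; constant AE rate λ per day (monthly rate ÷ 30.4); 14-day course, so 44 days counted (Day 0–43) and 183 − 44 = 139 days in the gap. A subject is affected if there is no event in the first 44 days and at least one between then and departure:

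p = 0.17 × e^(−44λ) × [139 − (1 − e^(−139λ))/λ] / 183

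At 0.1 per month, λ = 0.00329 and e^(−44λ) = 0.865. The bracket is 139 − 0.367/0.00329 ≈ 27.4, and 27.4/183 = 0.150. So p = 0.17 × 0.865 × 0.150 = 0.022.

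| AEs per month (assumed) | e^(−44λ) | bracket/183 | p | of 84 |
|---|---|---|---|---|
| 0.05 | 0.930 | 0.081 | 0.013 | 1.1 |
| 0.1 | 0.865 | 0.150 | 0.022 | 1.9 |
| 0.2 | 0.749 | 0.262 | 0.033 | 2.8 |

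**5. Subjects who stay but skip the dose.** Suppose all 17% are followed through the gap and the risk of an event in the gap is 10% (assumed). Then 84 × 0.10 = 8.4 subjects have such an event, and 8.4 × 0.83 = 7.0 are counted.

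**6. Pooling, Base Scenario.**

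| Arm | Initial treatment | Month 6 | Ivermectin reactions in TEAE count |
|---|---|---|---|
| K | selected regimen | ivermectin | yes |
| L | same as K | placebo | no |
| M | second regimen | undecided | depends |
| N1 | placebo | ivermectin | yes |

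L against N1 is flattered, because the control carries ivermectin reactions that L cannot have. K looks worse than L although both have the same initial regimen. In K against N1 both arms carry ivermectin. In the Alternate Scenario the contrast with N2 turns on a Month 6 choice not yet made.

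**The case against.** Much of the other side stands. Every Part 2 arm has a Month 6 IMP, active or placebo, so the nominal window is the same in all arms. AEs are collected to the end of participation (9.3.4.5), so an event outside the window is absent from the TEAE tables but not from the record. Section 10.8 also promises summaries of SAEs, deaths and AEs leading to discontinuation without saying that they are limited to TEAEs. Causality is assessed for each IMP (9.3.4.7), and TEAEs are tabulated by relationship. This corrects the pooling in part, but blinded investigator attribution does not replace a split window. SAP 1.0 announces a separate Part 2 SAP, which was not supplied and could define the window by dosing period. Until it does, the protocol's stated rule is the one it would inherit.

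Three stronger readings are tempting and not supported:

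- A reader might take the ratio of the long to the short window as the size of the distortion. It compares window lengths, not lost events: nothing that happens after departure can be recorded under any definition.
- A reader might infer that the rule always makes a harmful regimen look safer. The attrition effect has no direction between arms unless missing the dose differs by arm or is event-driven, and no figure in the documents shows either. The pooling effect flatters L but counts against K relative to L.
- A reader might infer that TEAE rates are the safety basis for choosing the Phase III regimen. Section 10.10 has the DSMB review safety and skin microfilaria data through Month 18, beyond any TEAE window.

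**Conclusion.** The point holds as a definitional fault in Protocol 10.8 for Part 2. As written, an event between about Day 37–44 and Month 6 is treatment-emergent only if a later dose is taken, and an event that leads to that dose being missed drops out of the TEAE tables. The numerical effect is modest: about 1–3 of 84 subjects per arm lose their only TEAE. That rests on the protocol's 17% loss by Month 6, uniform non-informative departure and an assumed 0.05–0.2 AEs per month. Event-driven departure would make it larger, but the documents give no basis for saying by how much. The pooling of ivermectin reactions follows from the allocation alone and affects L against N1 and K against L. It was not sized, because the documents give no reaction rate. The change is worth making before Part 2 opens; it does not undermine the trial.

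**What to change.** In Protocol 10.8 and in the Part 2 SAP, define TEAEs in Part 2 by dosing period:

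- **Initial regimen:** from the first intake of ABBV-4083, albendazole or matching placebo to 30 days after the last such intake, for all dosed subjects.
- **Month 6 dose:** from the ivermectin or placebo intake to 30 days after it, for subjects who took it.

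Tabulate AEs and SAEs outside these windows separately by arm. State that the SAE, death and discontinuation summaries are not restricted to TEAEs. A Month 3 event then falls outside both windows for everyone and is shown in the separate table whether or not the Month 6 dose follows.

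The sponsor should also reconcile related wording for Part 2. Section 3.5.2.2 ties the end of exposure to ABBV-4083 or albendazole, yet its toxicity criteria run to 30 days after the end of treatment and count events "considered as having a reasonable possibility of being related to any of the IMPs". Section 10.2 includes the Month 6 dose in treatment completion. The documents do not say which end of treatment applies to the cumulative toxicity count across Parts 1 and 2.

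The cost is wording and one extra set of tables. Onset dates are already collected, so data collection does not change.
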